This design aimed to investigate whether short, frequent bouts of aerobic exercise provide comparable cognitive benefits to longer, continuous sessions, potentially offering a more flexible and accessible option for individuals with time constraints.

3.

This study was conducted at the Faculty of Health Sciences, Gazi University, in the Department of Physiotherapy and Rehabilitation. Ethical approval was obtained from the Ethics Committee of Gazi University with the record number 2023- 1134 to conduct the study.

4. Participants

Participants in this study were **female individuals aged 18 to 25 years** who maintained a **sedentary lifestyle**, defined as taking fewer than 5000 steps per day. Additional inclusion criteria included being a **non-smoker**, having the **physical ability to walk on a treadmill**, maintaining a **work or school schedule compatible with the intervention schedule**, and providing **written informed consent**.

Exclusion criteria included having a **body mass index (BMI) of 30 kg/m² or higher**, a history of **neurological or severe cardiovascular conditions**, participation in another **regular exercise program** during the study period, any **physical limitation that would interfere with safe walking**, and **pregnancy**. These criteria were established to ensure the safety of participants and to maintain the homogeneity of the study population.

5. Interventions

Participants were randomly assigned to one of two intervention groups. The **experimental group** performed **three 10-minute walking sessions per day**, while the **active comparator group** completed **one continuous 30-minute walking session per day**. Both groups exercised **five days per week for six weeks**. The intensity of the exercise was standardized at **60% of the participant's maximum heart rate**, calculated using the formula $(220 - \text{age})$. Heart rate was continuously monitored using treadmill-integrated sensors and confirmed with pulse oximeter readings. Standardized warm-up and cool-down periods were integrated into both protocols.

6. Outcomes

The **primary outcome** of the study was the **change in Digit Symbol Substitution Test (DSST) scores** from baseline to post-intervention (6 weeks), reflecting improvements in **processing speed and executive function**.

Secondary outcomes included changes in performance on three subtests of the **Stroop Test**, which evaluated various aspects of cognitive function.

7. Sample Size and Power

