A power analysis was conducted using **G*Power 3.1** software. Based on an expected **effect size of 0.5**, a **power of 95%**, and a **significance level of 0.05**, the **minimum required sample size** was determined to be **34 participants**, with **17 in each group**. This calculation ensured that the study would be adequately powered to detect meaningful differences between groups.

8. Randomization

Randomization was performed using the online tool **Randomizer.org (Version 4.0)** to generate a computer-based random sequence, ensuring unbiased allocation of participants. A **1:1 allocation ratio** was used. Although participants were aware of their assigned walking schedules, **both the investigator supervising the training sessions and the assessor performing the cognitive tests were blinded to group assignment** to maintain objectivity in outcome evaluation.

9. Data Collection and Management

Cognitive function assessments were conducted at **baseline** and again **after the 6-week intervention**. All data were anonymized and stored securely in password-protected digital files accessible only to the research team. To ensure adherence, participants maintained **daily exercise logs**, and researchers conducted routine follow-ups throughout the intervention period. Any protocol deviations or dropouts were documented.

10. Statistical Analysis Plan (SAP)

Statistical analysis was performed using **SPSS version 24**. The **normality of distribution** for outcome variables was tested using the **Shapiro-Wilk test**. **Independent samples t-tests** were used to compare baseline values between groups, while **ANCOVA** was applied to adjust for any baseline differences when comparing post-intervention outcomes. **Paired t-tests** were used to evaluate within-group changes from baseline to post-intervention.

Effect sizes were calculated using **Cohen's d** to quantify the magnitude of observed changes. A **p-value of less than 0.05** was considered statistically significant. **Outliers** were identified through **z-score analysis** and **visual inspection of boxplots**. In cases of dropout or incomplete data, **listwise deletion** was applied, and only participants who completed both pre- and post-tests were included in the final analysis.

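### Section 7's 95% between-group power with 17 per group does not hold if the effect size of 0.5 is Cohen's d: power is 29% unadjusted and 32–65% by the planned ANCOVA for assumed correlations of 0.5–0.8

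*Protocol*

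**What the plan says.** Section 7 of the protocol reports a G*Power 3.1 calculation with these inputs: "Based on an expected effect size of 0.5, a power of 95%, and a significance level of 0.05". The minimum sample size "was determined to be 34 participants, with 17 in each group". The section concludes: "This calculation ensured that the study would be adequately powered to detect meaningful differences between groups". It does not give the statistical test, the effect-size metric, whether the test is one- or two-sided, or any baseline/post correlation.

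Three other statements bear on how to read this:

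- Section 6: the primary outcome "was the change in Digit Symbol Substitution Test (DSST) scores from baseline to post-intervention (6 weeks").
- Section 10, between-group analysis: "ANCOVA was applied to adjust for any baseline differences when comparing post-intervention outcomes".
- Section 10, reporting: "Effect sizes were calculated using Cohen's d to quantify the magnitude of observed changes". This is the only effect-size metric named in the protocol, and it is named for reporting results, not for planning.

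**The concern.** An effect size of 0.5 with 95% power normally calls for a much larger two-group trial than 34. The primary objective in section 1.3 is the comparison of the two walking protocols, and section 7 tells the reader that this comparison was given 95% power, meaning a 5% chance of missing the target difference.

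That assurance matters more than usual here. The secondary hypothesis in section 1.3 takes the absence of a significant difference as a sign that short bouts work as well as a continuous session. If real power is far below 95%, a non-significant result is likely even when a moderate difference exists, and the stated power makes that result look more informative than it is.

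**Working it through.** **Inputs from the protocol.** Effect size 0.5, power 0.95, alpha 0.05, n = 17 per group (section 7); 1:1 allocation (section 8); ANCOVA on post-intervention scores adjusted for baseline (section 10).

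**Inputs assumed.** Two-sided testing unless marked; baseline/post correlation r = 0.5, 0.7, 0.8; equal baseline and post SDs. The protocol gives none of these.

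**1. Trying to reproduce 34, with 0.5 as Cohen's d.** Normal approximation: n per group = 2(1.960 + 1.645)² / 0.5² = 2 × 12.996 / 0.25 = 103.97, so 104. The exact noncentral t gives 105 per group two-sided and 88 one-sided. The stated 17 is not reproduced.

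**2. Unadjusted power at 17 per group.** Noncentrality = 0.5 × √(17/2) = 1.458 on 32 df. Power is 29.3% two-sided and 41.4% one-sided. The detectable difference, two-sided, is 0.99 SD at 80% power and 1.28 SD at 95%.

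**3. Planned ANCOVA, d = 0.5 (31 df).** The residual SD is σ√(1−r²).

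- If 0.5 is in post-score SDs, the effective d is 0.5/√(1−r²).
- If 0.5 is in SDs of change, where the SD of change is σ√(2(1−r)), the effective d is 0.5 × √(2/(1+r)). This is a natural scale because the primary outcome is a change.

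| | r = 0.5 | r = 0.7 | r = 0.8 |
|---|---|---|---|
| Post-score SD: effective d | 0.577 | 0.700 | 0.833 |
| Power, two-sided | 37.1% | 50.7% | 65.3% |
| Power, one-sided | 50.1% | 63.7% | 76.8% |
| n per group for 95%, two-sided | 79 | 55 | 39 |
| Detectable at 95%, n = 17 | 1.11 | 0.91 | 0.77 |
| SD of change: effective d | 0.577 | 0.542 | 0.527 |
| Power, two-sided | 37.1% | 33.5% | 31.9% |
| Power, one-sided | 50.1% | 46.1% | 44.4% |
| n per group for 95%, two-sided | 79 | 90 | 95 |
| Detectable at 95%, n = 17 | 1.11 | 1.18 | 1.21 |

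On the post-score scale, two-sided power reaches 95% only at r of about 0.92. Simulated ANCOVA (20,000 runs per case) agrees: 36.3% and 63.5% on the post-score scale, and 36.4% and 31.2% on the change scale, at r = 0.5 and 0.8.

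**4. If 0.5 is Cohen's f.** For two equal groups d = 2f = 1.0, a difference of one SD. Two-sided ANCOVA with 17 per group then gives:

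- 81% if f is already on the covariate-adjusted SD;
- 90%, 98% and 99.7% at r = 0.5, 0.7 and 0.8 in post-score SDs (95% at r of about 0.62);
- 90%, 86.5% and 85% in SDs of change (95% only at r of about 0.23 or less).

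**The case against.** The strongest reply is that section 7 is under-specified rather than shown to be miscalculated. It never says that 0.5 is Cohen's d, and G*Power can return 34 for a design with two groups and two time points. By noncentral F with 1 and 32 df, a repeated-measures ANOVA between factor with f = 0.5 and assumed r = 0.2 gives 95.4% at 34. A group-by-time interaction with f = 0.25 and assumed r = 0.7 also gives 95.4% at 34. With f = 0.5 for the interaction, 34 exceeds 95% at every r tried from 0 to 0.8. Separately, 34 is the exact 80%-power answer for a two-sided paired t-test with d = 0.5 (80.8% at 34, 79.5% at 33), which would point to the wrong test and a wrong power label.

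These routes are arithmetically real, and it cannot be said that no calculation yields 34. They do not support what section 7 concludes, however. Each needs inputs the protocol does not state, and none is the ANCOVA in section 10. The repeated-measures routes also target larger effects. An interaction f of 0.25 in a two-by-two layout means cell deviations of ±0.25 SD, so a difference in change of 4 × 0.25 = 1.0 SD; f = 0.5 means 2.0 SD. The between-factor route concerns a 1.0 SD difference averaged over both time points, not a difference in change. The paired route is a within-group test and gives 81%, not 95%.

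It is also fair that the range r = 0.5 to 0.8 is an assumption. At r = 0.9 on the post-score scale, power would be 90%, still below 95%; on the change scale it would be 30.5%.

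**Conclusion.** The concern holds. If 0.5 is Cohen's d, 17 per group does not give 95% between-group power. The chance that the planned two-sided ANCOVA misses a true difference of that size is 35% to 63% (post-score SD) or 63% to 68% (SD of change) for r between 0.5 and 0.8, against the 5% that section 7 implies. This rests on reading 0.5 as d, on the assumed range of r, and on equal SDs at the two visits; one-sided testing does not close the gap over that range.

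If 0.5 is Cohen's f, the ANCOVA can reach 95% with 34, but for an effect twice as large and only on particular scales and correlations. On either reading, a reader cannot tell whether the trial was sized for a 0.5 SD or a 1.0 SD difference, and the unconditional statement of adequate between-group power is not supported. Section 10 limits the analysis to completers and section 7 states no allowance for dropout, so losses would lower power further.

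**What to change.** Keep 34 participants. In section 7:

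1. State the G*Power test, effect-size metric, sidedness and any correlation actually entered, and correct the stated power if those inputs do not return 34.
2. Add the power of the planned ANCOVA on DSST with its scale and assumptions labelled, for example: *For a between-group difference of 0.5 SD (two-sided alpha 0.05), 17 per group gives 29% power unadjusted. By ANCOVA, for an assumed baseline/post correlation rising from 0.5 to 0.8, power rises from 37% to 65% if 0.5 is in post-score SDs, or falls from 37% to 32% if it is in SDs of change. The detectable unadjusted d is about 1.0 at 80% power and 1.28 at 95%.*
3. If the original input was Cohen's f = 0.5, say that it represents a 1.0 SD difference.
4. Delete or qualify the closing sentence on adequate power for differences between groups.

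The cost is wording only, with no extra participants. The team must retrieve the original G*Power inputs and accept either a lower stated power or a larger stated target effect.
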